**The ending or interruption of study:**

Whenever in the course of study the patient can end his participation in study on basis of his decision. He will inform promptly his physician about this decision.

The recruitment of the subjects will be interrupted, when the preliminary analysis in the course of the trial shows significant difference in the incidence of endpoints between the study groups.

**Statistic:**

All subjects, participating in the study and completing the follow-up, will be involved into the statistical analysis. Considered rate of probands lost within follow-up is 2%.

The adequate methods of statistical evaluation of the study results will be used. Baseline demographic, clinical, angiographic, periprocedural data and results will be summarized using descriptive summary statistics.

Fischer's exact test will be used for comparison of qualitative variables between two groups. For comparison of quantitative variables Mann-Whitney U test, respectively Student's t-test will be used. Normality of data will be assessed with Shapiro-Wilk test. The value  $p < 0.05$  will be considered as statistically significant.

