**Design of clinical investigation**

Clinical, prospective, monocentric, randomized, open study

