**Study objective:**

The aim of the study is to prove

- that early discharge (within 72 hours) in selected group of patients with low risk of follow-up complications after myocardial infarction with elevations of ST segment, treated with primary percutaneous coronary intervention, is feasible and safe
- that early discharge is „non-inferior“ in comparison with the group of patients, discharged in a standard way accordingly with present practice and physician's decision (usually 4th-7th day), thus it is not associated with higher incidence of complications in 30th and 90th day after myocardial infarction

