**Study population:**

All subjects enrolled in the study.

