**Endpoints:**

Primary endpoint:

- Composite of incidence of death, reinfarction, unstable angina pectoris, stroke, unplanned rehospitalization, repeat target vessel revascularization and stent thrombosis in 90 days after myocardial infarction

Secondary endpoint:

- Complications associated with the puncture site requiring treatment in 30 days after myocardial infarction

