**Plan of study:**

**Number of probands:**

Enrollment of about 150-200 patients is planned

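### Limiting the analysis to patients who complete follow-up drops known primary-endpoint events in patients who later withdraw or are lost, and could drop deaths before day 90

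*Combined protocol and SAP*

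**What the plan says.** The only rule on who is analysed is in the Statistic section: "All subjects, participating in the study and completing the follow-up, will be involved into the statistical analysis". The next sentence allows for 2% of patients being lost. Completion of follow-up is not defined.

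Other sections bear on this rule:

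- Design of clinical investigation: "Clinical, prospective, monocentric, randomized, open study".
- The ending or interruption of study: "Whenever in the course of study the patient can end his participation in study on basis of his decision". Nothing is said about keeping data collected before a patient leaves.
- Endpoints: the 90-day primary endpoint begins "Composite of incidence of death, reinfarction, unstable angina pectoris, stroke", and goes on to unplanned rehospitalisation, target vessel revascularisation and stent thrombosis.
- Study population: "All subjects enrolled in the study". This is not called an analysis set and is not linked to the analysis or to assigned groups.
- Study objective: early discharge is to be shown non-inferior, "thus it is not associated with higher incidence of complications in 30th and 90th day after myocardial infarction".
- Number of probands: "Enrollment of about 150-200 patients is planned".

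The documents contain no intention-to-treat set, no censoring rule and no missing-data rule.

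**The concern.** Whether a patient completes follow-up is known only after randomisation and can depend on what has happened to that patient. Making it a condition of entry means the groups compared are no longer the groups that were randomised. In an open trial, knowledge of the assigned discharge policy can also influence who stays.

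The practical consequence is plain. A patient with a reinfarction on day 10 who withdraws on day 40 leaves both the numerator and the denominator, although the primary-endpoint event is on record. Deaths are less certain. The contrast with lost patients suggests that a known death may be meant to count, but a literal reading could exclude anyone who dies before day 90, and death is the first component of the composite.

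The claim to be supported is that complications are no more frequent with early discharge. That rests on the estimated difference and its interval. If events are discarded mainly from the early arm, harm is hidden. If mainly from the standard arm, early discharge looks worse than it is. With few events expected, a single discarded event shows in the result.

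**Working it through.** **Inputs from the documents.** Total enrolment about 150-200; allocation 1:1; expected loss 2%; primary endpoint at 90 days; Fisher's exact test for binary variables.

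**Assumptions.** The documents give no event rate. I take 5%, with a range of 2-10%, and equal arms of 75 or 100. The planned sample size cannot be reproduced, because no event rate, margin or power is stated.

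**Step 1: patients affected.** 0.02 × 150 = 3 and 0.02 × 200 = 4, leaving 147 or 196 analysed.

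**Step 2: events available.** At 5% the whole trial expects 0.05 × 150 = 7.5 to 0.05 × 200 = 10 events. One event is therefore 1/10 = 10% to 1/7.5 = 13% of the total, and moves an arm's rate by 1/100 = 1.0 point or 1/75 = 1.3 points.

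**Step 3: interval method.** The risk difference d is early minus standard, with Newcombe's 95% interval built from the Wilson limits (l, u) of each arm:

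- lower = d - √[(p₁ - l₁)² + (u₂ - p₂)²]
- upper = d + √[(u₁ - p₁)² + (p₂ - l₂)²]

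For 6/100 v 5/100 the Wilson limits in per cent are 2.78 to 12.48 and 2.15 to 11.18. The upper limit is 1.0 + √[(12.48 - 6)² + (5 - 2.15)²] = 8.1 and the lower is 1.0 - √[(6 - 2.78)² + (11.18 - 5)²] = -6.0.

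**Step 4: one known early-arm event discarded.**

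| Per arm | All randomised | After discarding |
|---|---|---|
| 100 | 6/100 v 5/100: +1.0 (-6.0 to 8.1) | 5/99 v 5/100: +0.1 (-6.8 to 6.9) |
| 75 | 5/75 v 4/75: +1.3 (-7.2 to 10.0) | 4/74 v 4/75: +0.1 (-8.2 to 8.4) |

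**Step 5: the planned loss, two patients per arm at 100 per arm.** Completers show 5/98 v 5/98: 0.0 (-6.9 to 6.9). The result in all randomised patients depends on who had events:

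| Lost patients with events | All randomised | Difference, points (95% CI) |
|---|---|---|
| Both early-arm patients only | 7/100 v 5/100 | +2.0 (-5.1 to 9.3) |
| Both standard-arm patients only | 5/100 v 7/100 | -2.0 (-9.3 to 5.1) |
| One in each arm | 6/100 v 6/100 | 0.0 (-7.2 to 7.2) |

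Over the assumed range of rates, the +2.0 case has an interval of -3.6 to 8.0 at 2% (4/100 v 2/100) and -7.0 to 11.0 at 10% (12/100 v 10/100).

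**Step 6: extremes.** If all four losses fall in one arm and all had events, the difference is 9/100 v 5/100 = +4.0 (-3.5 to 11.8), or the reverse, -4.0 (-11.8 to 3.5). When they are early-arm losses, completers would show 5/96 - 5/100 = 5.2% - 5.0% = +0.2 points.

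**Step 7: how likely.** If loss is unrelated to arm, all four fall in a given arm with probability 0.5⁴ = 6.25%, and two fall in each arm with probability 6/16 = 37.5%. If lost patients had the same 5% risk as the rest, the events missed would be 0.05 × 3 = 0.15 to 0.05 × 4 = 0.20.

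**The case against.** - **The text does not say that only completers are analysed, or that earlier data are deleted.** True, and the study population statement names all enrolled subjects. But the Statistic sentence is the one rule specific to the analysis, exclusion is its natural reading, and nothing elsewhere keeps known events. At best the two sections conflict.

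- **A known death is not a lost patient, and excluding early deaths would defeat the endpoint.** This is a reasonable reading of the intent, so the point on deaths is put only as a possibility. The wording still leaves it open.

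- **The ±2.0 and ±4.0 cases suppose events among lost patients that may never be known.** This stands. Such events reach the main analysis only if they are known. If they are not, and the patients are counted as event-free, the result is 5/100 v 5/100 = 0.0 (-6.8 to 6.8), hardly different from the completers' 0.0 (-6.9 to 6.9). Only sensitivity analyses would then show the possible range. The single-event cases in step 4 concern known events and are unaffected.

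- **The effect is small unless loss is related to events, and nothing in the documents shows that it is.** Also true. The ±4.0 extreme further needs an event in all four patients, which at an independent 5% risk has probability 0.05⁴, about 6 in a million. Fisher's test stays non-significant in every case above (p = 1.0 before and after in step 4), and with no stated margin no non-inferiority conclusion can be shown to reverse. But the 2% is a planning figure and not a ceiling, and a non-significant Fisher test does not establish non-inferiority. These points limit the likely size. They do not justify discarding recorded endpoint events.

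**Conclusion.** The concern holds. Followed as written, the rule removes known primary-endpoint events in patients who later withdraw or are lost, and it leaves the status of deaths before day 90 unclear. This is a fault in a stated rule for the primary analysis, not merely a missing detail, and it should be corrected before the data are analysed.

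Each known event discarded shifts the estimated difference by about 1.0 point at 100 per arm or 1.3 points at 75 per arm, in either direction. At the planned 2% loss, plausible shifts are up to about 2 points, with an unlikely extreme of about 4. These sizes rest on the assumed 5% event rate (range 2-10%), equal arms, and loss that is related to events. If loss is unrelated to events, the expected effect is negligible. Confidence is high that the rule is wrong; how far it would move the result cannot be known from the documents.

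**What to change.** Replace the sentence in the Statistic section with wording such as:

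> All randomised patients are analysed in the group to which they were assigned. Death and any component event known to have occurred by day 90 count, whether or not the patient later withdrew or was lost. For patients who withdraw, events up to withdrawal count, and later events count where continued follow-up is permitted.

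Then:

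1. State how patients with no known event and unknown day-90 status enter the main analysis. One option is to keep them in the denominator as event-free and report their number by arm. That option lowers the observed rates and slightly narrows the interval, which mildly favours a non-inferiority claim, so it should not stand without item 2.
2. Add two sensitivity analyses for these patients: early-arm unknowns as events with standard-arm unknowns as event-free, and the reverse.
3. Keep the completer analysis as supportive.
4. Align the Study population section with the new wording.

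The planned Fisher comparison can stay; Kaplan-Meier estimates are optional.

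The cost is a paragraph and two tables, and possibly a slightly less favourable estimate. The change needs event dates and day-90 status for each patient. The documents contain no data-collection list, so whether these are already recorded cannot be checked.

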## **Introduction:**

Within past decades we can observe the clear trend towards the shortening of the hospital stay in patients admitted with the diagnosis of myocardial infarction with ST segment elevations (STEMI).

The current Guidelines of European Society of Cardiology for the management of acute myocardial infarction with ST-segment elevation, released in 2012, state, that in the selected patients may be considered (class of recommendation IIb) early discharge (after approximately 72 hours), if adequate follow-up is arranged.

Level of evidence of cited recommendation is B, i.e. it is based on data, derived from a single randomized clinical trial or large non-randomized studies.

The overview of literature on this topic shows non-uniform methodology of these works and heterogeneous features of studied populations (3 – 63% fulfilled criteria for early discharge!)

In the PAMI II study the low risk was defined as following: age <70 years, left ventricle ejection fraction >45%, one- or two-vessel disease, successful percutaneous coronary intervention (PCI) and no persistent arrhythmias.

In Czech Republic the issue of early discharge was investigated in PRASGUE 5 study (Jirmar et al., 2008), which after pilot phase randomized 56 low risk probands with STEMI, discharged even the next day after successful PCI. The strict inclusion criteria (fulfilled only 3% patients with acute STEMI) included age < 75 years, optimal result of primary PCI, one-vessel disease, left ventricle ejection fraction > 40%, place of residence < 20km, exclusion criteria involved patients after Q-MI, haemodynamically or rhythmically instable, with recurrent chest pain or clinical/laboratory findings requiring additional evaluation.

Followed endpoints were death, reinfarction, stroke, instable angina pectoris, repeat target vessel revascularization, local groin complications requiring treatment and left ventricle ejection fraction within 30 days. This study also showed, that very early discharge in clearly defined group of patients is safe, there was just one rehospitalization due to non-cardiac cause in the group of 37 patients, discharged the next day after MI, there was no other serious event in study population.

By the verification of safety of early discharge this study wants to confirm the applicability of presented conclusions even in the regular clinical practice in our circumstances.

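### The aim is to prove non-inferiority, but the plan gives no margin or non-inferiority rule, and its only applicable test is a test for difference

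*Combined protocol and SAP*

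**What the plan says.** **Study objective.** There are two aims: that early discharge is feasible and safe, and that it is non-inferior to discharge under present practice. The second is explained only in words, with no number: "thus it is not associated with higher incidence of complications in 30th and 90th day after myocardial infarction".

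**Endpoints.** The primary endpoint is a binary composite running from death and reinfarction through "unplanned rehospitalization, repeat target vessel revascularization and stent thrombosis in 90 days after myocardial infarction". The only endpoint set at 30 days is the secondary one: "Complications associated with the puncture site requiring treatment in 30 days after myocardial infarction".

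**Number of probands.** "Enrollment of about 150-200 patients is planned", without an event rate, power or margin behind it.

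**Statistic.** No test is assigned to the composite by name. For categorical data, Fisher's "exact test will be used for comparison of qualitative variables between two groups", and p < 0.05 counts as significant. Sidedness and confidence level are not given. Otherwise there is a general assurance: "The adequate methods of statistical evaluation of the study results will be used".

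**The ending or interruption of study.** Recruitment is interrupted if a preliminary analysis "shows significant difference in the incidence of endpoints between the study groups". This too is framed as a difference.

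**The concern.** Fisher's exact test has equality of the two risks as its null hypothesis. Rejecting that null shows a difference. Failing to reject it shows nothing about how large an excess could still be present. A non-inferiority claim needs the reverse: a null hypothesis that the excess is at least some stated margin, and data that reject it. The plan states neither the margin nor the rule.

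The risk is that a non-significant p-value will be reported as proof of non-inferiority. The plan does not say so outright. However, it describes non-inferiority as the absence of a higher incidence and offers only tests for difference, so this is the likely reading. That reading cannot tell no excess from too few patients to see one, and a smaller trial passes it more easily. If Fisher's test is not meant for the composite, the primary endpoint has no named test at all.

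Day 30 adds a gap. The non-inferiority statement covers days 30 and 90, but the composite is defined only at 90 days.

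**Working it through.** **1. Can the planned size be reproduced?** No. That needs a margin, an event rate, a power and a sidedness, and none is stated. Everything below is illustrative and does not decide the finding.

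**2. Inputs.**
- From the documents: 150-200 patients, 1:1 allocation, 2% loss, p < 0.05.
- Assumed: equal arms of 75 or 100 analysed (150/2 and 200/2), a two-sided test, and a range of 90-day control rates.
- The only rate in the documents is in the Introduction: in the cited next-day-discharge study "there was just one rehospitalization due to non-cardiac cause in the group of 37 patients", with no other serious event. That is 1/37 = 2.7% (Wilson 95% CI 0.5% to 13.8%), over 30 days and in a more strictly selected population.

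**3. How often would a real excess be non-significant?** For n per arm, control risk p and early-discharge risk q, sum over all outcome pairs:

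P(non-significant) = Σᵢ Σⱼ Bin(i; n, q) · Bin(j; n, p) · 1[Fisher p(i, j) ≥ 0.05]

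| Control rate p | True doubling (q = 2p), n = 75 / 100 | True 10-point excess (q = p + 0.10), n = 75 / 100 |
|---|---|---|
| 3% | 95% / 91% | 48% / 31% |
| 5% | 87% / 81% | 56% / 41% |
| 10% | 68% / 56% | 68% / 56% |
| 15% | 47% / 33% | 74% / 64% |
| 20% | 29% / 16% | not computed |

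If p ≥ 0.05 were read as non-inferiority, a true 10-point excess would pass 31% to 74% of the time at control rates of 3-15%. Under a rule that requires the upper Newcombe 95% limit to be below 10 points, the same excess passes 2.2% to 2.6% of the time.

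**4. One possible result.** Early 12/100, standard 5/100, difference 7.0 points. Fisher p = 0.126. The Wilson limits are 7.0% to 19.8% and 2.2% to 11.2%. The Newcombe limits are:

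- lower: 7.0 − √[(12 − 7.0)² + (11.2 − 5)²] ≈ −0.9 points
- upper: 7.0 + √[(19.8 − 12)² + (5 − 2.2)²] ≈ +15.3 points

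The result is not significant, yet it is compatible with an excess of 15 points.

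**5. What could 150-200 patients support?** Exact power of the Newcombe rule when the true rates are equal:

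| True rate | 5-point margin, n = 75 / 100 | 10-point margin, n = 75 / 100 |
|---|---|---|
| 3% | 32% / 41% | 85% / 93% |
| 5% | 24% / 31% | 72% / 83% |
| 10% | 17% / 20% | 51% / 62% |

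With 2% loss (73 / 98 per arm) these change by at most 5 points. For a 10-point margin, power becomes 79.8% / 92.7% at 3% and 67.6% / 83.6% at 5%.

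For 80% power at rates of 3%, 5% and 10%, in steps of 10 per arm, a 5-point margin needs about 220, 320 and 580 per arm. A 10-point margin needs about 70, 100 and 150. These are approximate because exact power does not rise smoothly with n: at 3% and a 10-point margin it is 80.7% with 70 per arm and 79.8% with 73.

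**The case against.** - **The p ≥ 0.05 reading is inferred.** This is fair: no section states it. It is a risk the plan leaves open. The missing margin and rule are matters of text and need no inference.
- **The contrast of 31-74% with 2-3% is partly circular.** Correct. The assumed excess equals the assumed margin, so a figure near 2.5% is simply the rule's nominal one-sided error at its own boundary. What the contrast shows is that a margin-based rule controls that error and a non-significance reading does not.
- **The general assurance in the Statistic section might cover the proper method.** It names no margin, interval or hypothesis, and leaves all three to be chosen after the data are seen in an open study.
- **Day 30 may refer to the puncture-site endpoint.** That is a possible reading. The text is ambiguous, so this part needs clarification.
- **The rates are assumed and the anchor is thin.** True. The figures show scale only. Simple randomization will also rarely give exactly equal arms.
- **The planned size may be adequate.** It may be at the upper end: with 98 per arm and a 10-point margin, power exceeds 80% at rates of 3% and 5%. At the lower end (73 per arm) it just misses 80% at 3% and clearly misses at 5%. The size is unsupported, but it is not shown to be wrong.

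**Conclusion.** The concern holds and must be fixed. The stated aim is non-inferiority, the only applicable named method tests for a difference, and no margin or decision rule exists. Followed as written, the plan cannot validly reach its non-inferiority conclusion. The feasibility and safety aim can still be described.

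This follows from the text and needs no assumed rate. The practical size does depend on assumptions: 75 or 100 analysed per arm, a two-sided test, and control rates of 3-20% for a doubling or 3-15% for a 10-point excess. Within those ranges, a doubling would be non-significant between 16% and 95% of the time, and a 10-point excess between 31% and 74%. The lower the event rate, the more easily a doubling goes unseen.

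**What to change.** 1. **Statistic.** Make the primary analysis the 90-day risk difference (early minus standard) with a two-sided 95% confidence interval by one prespecified method, for example Newcombe or Miettinen-Nurminen. State that p ≥ 0.05 will not be read as non-inferiority. Fisher's test can stay for baseline and descriptive comparisons.
2. **Margin.** Declare non-inferiority only if the upper limit is below a margin justified on clinical grounds and not derived from the available sample. Because the study is open, fix and date the margin before any comparison of outcomes, including the preliminary analysis.
3. **Day 30.** Say whether it belongs to the non-inferiority claim. If it does, define a 30-day composite under Endpoints and apply the same rule. If not, label it descriptive, so that Study objective and Endpoints agree.
4. **Number of probands.** State the precision that 150-200 patients give over a range of event rates labelled as assumptions.
5. **Fallback.** If no clinically acceptable margin can be supported at this size, replace the aim of proving non-inferiority with estimating the difference and its 95% confidence interval.

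The cost is rewording of four sections, with no new data items. The fallback means a more modest claim. A margin as narrow as 5 points would cost much more: about 220 to 580 per arm at rates of 3-10%, well beyond the planned enrolment.

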**Open access to source data / documents:**

The investigator in case of need and submission of written request gives access to source data/documents for the purposes of clinical investigation monitoring to ethics committees or controlling authorities inspection.

**Data manipulation and retaining of records:**

All information concerning the studied subjects will be kept in confidence to the extent, appropriate laws and directions. Medical records and information, obtained within clinical investigation, can be studied by doctors or medical staff practicing the study, local healthcare authorities, auditors, ethics committees. No personal data of subjects participating in study will be published. Patients will sign the informed consent with collection, transmission, processing and archiving of personal data, including state of health in the connection with conducted study.

